9.8.1. Treatment Emergent Adverse Events

Adverse events (AEs) will be coded by Medical Dictionary for Regulatory Activities (MedDRA) and their severity will be graded according to the NCI Common Terminology Criteria for Adverse Events (CTCAE, version 5.0) [13]. The analysis will focus on the events emerged during treatment and on those worsened on treatment in comparison to the baseline condition (TEAE, treatment emergent adverse events). For each dose level and overall, the incidence of AEs will be grouped by System Organ Class (SOC) and preferred term or by preferred term only. Each patient will be counted once according to the worst grade reported throughout the whole treatment period for each SOC and/or for each preferred term.

AEs will be summarized by descending frequency of SOC and preferred term, or preferred term only, depending of the analysis reported, unless otherwise specified. In addition, serious AEs, AEs with severity grade 3-5, AEs leading to treatment withdrawal, AEs leading to treatment reduction, omission, delay, infusion interrupted, infusion rate slowed, and AEs related to study treatment, will be analysed separately. A summary table of number and percentage of each possible AE categories (e.g. all AE, related AEs, serious, serious related etc.) will be also provided.

The analysis of number of occurrences of non-serious AEs, serious AEs, serious related to NMS-01940153E AEs and serious AEs leading to death by SOC and preferred term will be performed

Statistical Analysis Plan

only for regulatory purpose since these data have to be recorded in EudraCT/Clingov databases at end of the trial. This analysis will be only reported as appendix in the CSR.

9.8.2. Dose Limiting Toxicities

A DLT will be defined as any of the adverse events described in MPSA-153-001 Clinical Protocol Section 5.2.1 occurring in Cycle 1, during Phase I dose escalation, for which the relationship to NMS-01940153E cannot be definitely excluded. Toxicities are to be graded according to the NCI CTCAE version 5.0 [13]. In particular:

Hematological Toxicity

- Neutropenia Grade 4 lasting >7 days or Grade 4 of any duration associated with Grade ≥ 2 infection
- Febrile neutropenia ANC <1000/mm³ and a single temperature of >38.3 degrees C or a sustained temperature of ≥ 38 degrees C for more than one hour.
- Thrombocytopenia Grade 3 associated with any grade bleeding or Grade 4
- Anaemia Grade ≥ 4

Non-Hematological Toxicity

- Nausea, vomiting or diarrhea Grade ≥ 3 despite optimal treatment
- Signs of potential severe drug-induced liver injury as assessed according to Hy's law: Alanine aminotransferase (ALT) or aspartate aminotransferase (AST) >3 ULN and total bilirubin >2 ULN in the absence of cholestasis (alkaline phosphatase [ALP] <2 ULN) and no other reason can be identified.
- Any other non-hematological toxicities: Grade ≥ 3 toxicities unless clear alternate etiology is documented by the investigator and except:
 - asymptomatic Grade 3 electrolyte changes that can be successfully supplemented (e.g., hypokalemia) and resolve/recover to baseline within 72 hours
 - Grade 3 fatigue that improves to \leq Grade 2 in no more than 5 days
 - alopecia

Other significant toxicity

- Failure to complete the first cycle of treatment with at least 66% of the planned total dose due to toxicity possibly related to the study medication
- Failure to start Cycle 2 for more than 1 week (day 36 or later) due to persistent Grade ≥ 2 toxicities possibly related to the study medication, excluding fatigue
- Any toxicity that is possibly related to the study medication and requires the withdrawal of the patient from the study during the DLT observation period

Statistical Analysis Plan

- Any on-study death not clearly due to underlying disease or extraneous causes

For the Phase I part only, first cycle DLT analysis will be performed on the dose-limiting toxicity evaluable set. For each dose level, patients who experienced a DLT during the first cycle of treatment and type of DLT experienced, will be reported in a data listing.

9.8.3. Deaths

Frequency of deaths will be presented by study phase and dose level and relationship to the study treatment and according to the time since treatment discontinuation

Date of death, primary reason for death and relation to study treatment will be provided in a data listing together with selected dosing information (dose level, date of first / last dose administration, number of cycles received of study treatment, time from last dose administered). Primary reason for death and time in days of occurrence of death since last dose of study treatment administered, will be tabulated.

9.8.4. Clinical Laboratory Evaluations

Quantitative laboratory variables (hematology, blood chemistry, coagulation) will be summarized using mean, standard deviation, minimum, maximum and median, by study phase and dose level at each visit. At each cycle, the same descriptive statistics of within-subject changes from baseline measurements will be also presented.

The following laboratory data will be graded from Grade 1 up to Grade 4 according to the NCI CTCAE scale (version 5.0): hemoglobin (except Grade 4 for anemia), platelets, white blood cells (except Grade 4 for leukocytosis), neutrophils, lymphocytes, glucose (graded only for glucose decrease; i.e. hypoglycemia), sodium (graded only for sodium increase; i.e. hypernatremia), potassium (graded only for potassium increase; i.e. hyperkalemia), total calcium after correction with albumin, magnesium, creatinine, albumin (except Grade 4), aspartate aminotransferase (AST), alanine aminotransferase (ALT), alkaline phosphatase (ALP), gamma-GT (GGT), total bilirubin and lactate dehydrogenase (LDH) (only Grade 1 possible). For lab tests reported in the NCI CTCAE scale for which the grading system is based mainly on clinical assessments, the grade will not be calculated. For example, this applies to eosinophils, glucose (hyperglycemia), phosphorus (both hyperphosphatemia and hyperphosphatemia), sodium (hyponatremia), potassium (hypokalemia) and INR.

Laboratory abnormalities will be summarized in frequency distribution tables by study phase, dose level and treatment period (i.e. treatment Cycle 1, Cycle >1 and the whole treatment period).

For each parameter graded according to NCI CTCAE scale, patients will be classified based on the maximal severity grade observed during the analyzed time-window. Changes of severity grade

Statistical Analysis Plan

vs. baseline will be evaluated by shift tables. Selected laboratory parameters will be further explored by analyzing the nadir/zenith values, the time to nadir/zenith and the time to recovery after nadir/zenith, as clinically appropriate.

For the laboratory data not graded by the NCI CTCAE scale, a cross tabulation of on treatment worst finding versus baseline finding will be presented reporting the number of patients with values within or out of the normal range (i.e. hypo and/or hyper depending of the lab test considered), during the analyzed time-window. This analysis will be performed for the following lab tests: erythrocytes, monocytes, eosinophils, basophils, glucose (only for hyperglycemia), phosphorus, sodium (only for hyponatremia), potassium (only for hypokalemia), urea, blood urea nitrogen (BUN), total protein, unconjugated bilirubin.

Laboratory results (hematology, blood chemistry, coagulation) will be listed for all treated patients by study phase, assigned schedule and dose level at each visit. All other parameters collected on the eCRF, i.e. urinalysis and pregnancy tests, will be listed in dedicated listings presenting all corresponding collected information on the eCRF.

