11.5.2. Laboratory Safety Assessments

Laboratory safety assessments will include repeated evaluation of hematology, biochemistry and coagulation parameters, urinalyses and pregnancy test, according to timing reported in Section 7, Schedule of Events (Table and related footnotes). Investigators may order additional blood tests for planning treatment administration, dose modification, or further evaluation of adverse events.

The following laboratory parameters will be used to monitor safety:

- *Hematology* (local laboratory) includes: hemoglobin (Hb), red blood cells (RBC), platelet (PLT) and white blood cells (WBC) with differential count (neutrophils, lymphocytes, monocytes, eosinophils and basophils). The assessment is mandatory, at screening (≤ 7 days from treatment start). During treatment on Phase I, hematology should be done from cycle 1 to cycle 3, on days 1, 8, 15, 22 and, from cycle 4 onward, on days 1, 8, 15; during treatment on Phase II, hematology should be done on cycle 1, on days 1, 8, 15, 22; from cycle 2 onward, on days 1, 8, 15; at cycle 2, in case neutropenia Grade ≥ 2 is observed, repeat the hematological evaluation also at day 22. In case of cycle delay due to toxicity and/or if clinically indicated, additional assessments should be done as per medical judgment; hematology should be repeated at the start of the delayed cycle. All hematology assessments performed during the treatment period can be done the day before the scheduled one; on days of treatment administration, sampling should be performed and results should be available before the start of NMS-01940153E infusion. Hematology should be performed also at end of treatment (EoT) and 28-days follow up visits. Note: at Cycle 1 Day 1, hematology does not need to be repeated before study drug administration if it was performed at screening within 24 hours from treatment start.

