- *Blood chemistry* (local laboratory) includes: glucose, electrolytes (Na, K, Ca, P, magnesium), urea or BUN (Phase II), serum creatinine, creatinine clearance (calculated with Cockcroft-Gault equation), total protein, albumin, aspartate aminotransferase (AST/SGOT), alanine aminotransferase (ALT/SGPT), gamma-GT, total bilirubin, unconjugated bilirubin, alkaline phosphatase (ALP), lactate dehydrogenase (LDH). The assessment is mandatory, at screening (≤ 7 days from treatment start). During treatment on Phase I, blood chemistry should be done from cycle 1 to cycle 3, on days 1, 8, 15, 22 and, from cycle 4 onward, on days 1, 8, 15; during treatment on Phase II, blood chemistry should be done on cycle 1, on days 1, 8, 15, 22 and, from cycle 2 onward, on days 1, 15. In case of cycle delay due to toxicity and/or if clinically indicated, additional assessments should be done as per medical judgment; blood chemistry should be repeated at the start of the delayed cycle. All blood chemistry assessments performed during the treatment period can be done the day before the scheduled one; on days of treatment administration, sampling should be performed, and results should be available before the start of NMS-01940153E infusion. Blood chemistry should be performed also at EoT and 28-days follow up visits. Note: at Cycle 1 Day 1, blood chemistry does not need to be repeated before study drug administration if it was performed at screening within 24 hours from treatment start.

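### In Phase II the worst-grade laboratory columns for Cycle 1 and Cycle >1 are not comparable: sampling days and the number of cycles pooled both differ, and the resulting artefact can run in either direction

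*SAP*

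**What the plan says.** SAP 9.8.4 sets out laboratory frequency tables "by study phase, dose level and treatment period (i.e. treatment Cycle 1, Cycle >1 and the whole treatment period"). For graded parameters, "patients will be classified based on the maximal severity grade observed during the analyzed time-window". Selected parameters are to be explored further by "analyzing the nadir/zenith values, the time to nadir/zenith and the time to recovery after nadir/zenith, as clinically appropriate". Protocol 12.3.6 plans the same period tables. The secondary safety endpoint (Protocol 4.2.2, SAP 3.2.2) is framed by first and later cycles of therapy.

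Dosing is on days 1, 8 and 15 of each 28-day cycle (Protocol 9.2.1). For Phase II, Protocol 11.5.2 says "hematology should be done on cycle 1, on days 1, 8, 15, 22; from cycle 2 onward, on days 1, 8, 15". In Cycle 2, if Grade ≥2 neutropenia "is observed, repeat the hematological evaluation also at day 22". For chemistry, "blood chemistry should be done on cycle 1, on days 1, 8, 15, 22 and, from cycle 2 onward, on days 1, 15". Coagulation follows the chemistry days (Table 4, footnote 13).

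| Phase II | Cycle 1 | Cycle 2 | Cycle 3 onward |
|---|---|---|---|
| Hematology | days 1, 8, 15, 22 | days 1, 8, 15; day 22 only after Grade ≥2 neutropenia | days 1, 8, 15 |
| Chemistry, coagulation | days 1, 8, 15, 22 | days 1, 15 | days 1, 15 |

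Phase I is different: "During treatment on Phase I, hematology should be done from cycle 1 to cycle 3, on days 1, 8, 15, 22", and day 22 is dropped only from Cycle 4.

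**The concern.** A worst grade is a maximum, so it depends on how many samples are taken and on which days. Day 22 is the only scheduled sample between the third dose and the next cycle. In Phase II the first routine count after the day 15 dose comes 7 days later in Cycle 1 and 14 days later (next day 1) from Cycle 2. A low value that recovers in between is seen in one column and missed in the other. The Cycle 2 day 22 count depends on the outcome being measured. Against this, the Cycle >1 column takes the maximum over a number of cycles that varies by patient, which raises it.

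The stake is the description of how toxicity evolves with continued treatment. Protocol 5.3 names dose-related neutropenia as the major safety feature, and Protocol 3.6 records related Grade 3 neutropenia in 4 of 7 patients at the top dose of the first-in-human study. The AE tables do not fill the gap, because Protocol 11.5.1.8 excludes uncomplicated, asymptomatic laboratory findings from AE reporting. Given the wording of the secondary endpoint, readers will set these two columns against each other.

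**Working it through.** The plan gives no figure for this point, so there is none to reproduce. The question is what each column would show if true toxicity were identical in every cycle.

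**Inputs.** The sampling days are those tabulated above. Let a, b, c, d be the chances of Grade ≥3 on day 8, day 15, day 22 and the next cycle's pre-dose day 1. The documents give none of these; all values are assumptions. Let k be the number of later cycles. Days and cycles are taken as independent. End-of-treatment samples, unscheduled samples and the Cycle 2 trigger are left out.

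**Formulas.**
- Cycle 1: 1 − (1−a)(1−b)(1−c)
- Cycle >1, hematology: 1 − [(1−a)(1−b)(1−d)]^k
- Cycle >1, chemistry: 1 − [(1−b)(1−d)]^k

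**Numbers**, for a, b, c, d = 0.05, 0.10, 0.20, 0.05:
- Cycle 1: 1 − 0.95×0.90×0.80 = 31.6%
- Hematology, k = 1: 1 − 0.95×0.90×0.95 = 18.8%
- Chemistry, k = 1: 1 − 0.90×0.95 = 14.5%

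| a, b, c, d | Parameter | Cycle 1 | k=1 | k=2 | k=3 | k=4 |
|---|---|---|---|---|---|---|
| 0.05, 0.10, 0.20, 0.05 | Hematology | 31.6% | 18.8% | 34.0% | 46.4% | 56.5% |
| same | Chemistry | 31.6% | 14.5% | 26.9% | 37.5% | 46.6% |
| 0.02, 0.05, 0.20, 0.02 | Hematology | 25.5% | 8.8% | 16.8% | 24.1% | 30.7% |
| same | Chemistry | 25.5% | 6.9% | 13.3% | 19.3% | 24.9% |

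In the first pattern the fall at one later cycle is 13 to 17 points. It has become a rise by two later cycles for hematology and by three for chemistry.

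**No day 22 peak.** Take an equal 10% chance at each one-week-post-dose sample and ignore day 1. Cycle 1 gives 1 − 0.9³ = 27.1%. Hematology in Cycle >1 gives 1 − 0.9² = 19.0% at k = 1 and 1 − 0.9⁴ = 34.4% at k = 2. Chemistry gives 10.0% at k = 1 and reaches 27.1% at k = 3.

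**Relaxing independence.** A simulation gave each patient the same underlying curve in every cycle, with assumed curve parameters and within-patient variation on the log scale (hematology schedule):
- Nadir on days 20 to 24, log-SD 0.2: 13–20% in Cycle 1 against 0–3% in Cycle >1, even with six later cycles.
- Same nadir days, log-SD 0.35, six later cycles: the gap narrows, for example 19.7% against 15.6% for a day 20 nadir.
- Nadir on day 15, log-SD 0.2: 19.4% against 19.4% with one later cycle, and a rise to 37.5% with six.

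**Matched days, one cycle at a time.** With the first pattern, hematology on days 8 and 15 gives 1 − 0.95×0.90 = 14.5% in Cycle 1 and in any later cycle. Chemistry on day 15 gives 10% in each. Crediting the next pre-dose day 1 to the cycle just ended gives 18.8% and 14.5%, again equal across cycles. The artefact disappears.

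**The case against.** A reader might infer that the scheme will make toxicity appear to fall after Cycle 1. The documents do not support a fixed direction. The planned Cycle >1 column is a maximum over all later cycles, so any comparison of Cycle 1 with a single later cycle describes a column the SAP does not plan. The nadir day is not stated either; if it falls on or before day 15, the missing day 22 matters little. This part of the objection stands.

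A reader might also infer that nadir depth and recovery time will be compared between the two columns. SAP 9.8.4 describes those analyses as exploratory and does not say they are split by cycle. Confining them to Phase II Cycle 1 would discard nadirs actually observed on days 8 and 15 of later cycles.

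Nor can one say that the plan has no rule for unequal sampling. SAP 8.2 places all conventions in a separate appendix that was not available.

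Finally, SAP 9.8.4 already summarizes quantitative values by visit, and the listings show every result. That allows like-for-like reading of means and ranges, but it does not give the proportion of patients at each grade on matched days. The consequence is limited in any case: no test is planned, Phase I DLT assessment is unaffected, and the Phase II hold rule (SAP 5.2) counts patients with Grade 4 adverse events, not this comparison.

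**Conclusion.** The point holds as one of non-comparability. Followed as written in the SAP, Phase II will show two adjacent worst-grade columns that differ in sampling days, in outcome-dependent sampling (Cycle 2 hematology) and in the number of cycles pooled. With constant true toxicity, the assumed patterns give anything from a fall of about 17 points (chemistry or hematology, one later cycle) to a rise of 15 points or more (hematology, three or four later cycles in the first pattern). A few later cycles or a nadir near day 22 favour a fall; several later cycles or an earlier nadir favour a rise.

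These sizes rest on assumed daily risks and, in the closed form, on independence; they show what is possible and do not predict what will be seen. The problem lies mainly in Phase II. Phase I has it in part, since day 22 stops at Cycle 4 and later cycles are pooled there too. If the separate appendix already contains a common-day rule, a cross-reference in SAP 9.8.4 would settle the matter.

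**What to change.** Keep the Cycle 1, Cycle >1 and whole-period tables, which the protocol specifies. Add to SAP 9.8.4:

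- A Phase II graded table by individual cycle, with patients treated in that cycle as denominator, restricted to days routinely sampled in every cycle: hematology days 8 and 15, chemistry day 15. Use day 15 for coagulation as well wherever INR abnormalities are tabulated, since the SAP does not grade INR.
- Optionally, the next cycle's pre-dose day 1 credited to the cycle just ended. It exists only for patients who start that next cycle, so show it as an extension.
- Cycle 1 day 22 results shown separately.
- A statement that any first-versus-later-cycle conclusion on laboratory toxicity rests on this table.
- Nadir, time to nadir and recovery reported separately for cycles with a routine day 22 sample (Phase II Cycle 1; Phase I Cycles 1 to 3) and cycles without, keeping the later-cycle data.

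The cost is SAP wording and extra programming; no blood sample is added. Matching days does not remove differences between cycles caused by dose reduction or attrition, and a footnote should say so.

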9.8.5. Other Safety Evaluations (e.g. Vital signs, ECG, ECOG PS, etc.)

All vital sign parameters (i.e. systolic blood pressure, diastolic blood pressure and pulse), weight and BSA will be summarized using descriptive statistics (mean, standard deviation, median, minimum, and maximum) of actual values and changes from baseline for each cycle with a minimum number of patients with at least one valid assessment. The maximum on-treatment change from baseline will be calculated and categorized by systolic blood pressure (SBP) and diastolic blood pressure (DBP) measurements. Additionally, the worst assessment on treatment versus baseline, defined in terms of classes (i.e. normal BP: SBP < 140 mmHg and DBP < 90 mmHg; abnormal BP: SBP \geq 140 mmHg and/or DBP \geq 90 mmHg), will be summarized by shift table. The ECOG PS shift from baseline to highest score during the on-treatment period will be also summarized.

Descriptive summaries of actual values and changes from baseline will be presented, for both Phase I and Phase II, for corrected Fridericia QT interval (QTc). The following additional ECG parameters collected in triplicate for patients enrolled in Phase II, will be also analyzed: sinus rhythm, heart rate (HR), RR interval, PR interval, QRS interval, QT interval. The maximum on-treatment change from baseline will be calculated and categorized by QTc (for both Phase I and Phase II), HR, RR, PR and QRS (only for Phase II) measurements. Absolute frequency and percentage of treated patients with at least one clinically significant ECG abnormality during the treatment period will be summarized by category of ECG abnormalities.

Additionally, for all ECG parameters, the worst assessment on treatment versus baseline, defined in terms of classes, will be summarized by shift table. Frequency and percentage of treated patients with at least one clinically significant ECG abnormality during the treatment period will be summarized by category of ECG abnormalities.

Vital signs data, weight, BSA, ECOG PS and ECG data (both quantitative and qualitative) will be also presented in data listings.

9.9. Exploratory Analyses

Exploratory analysis on the relationship between AFP levels and treatment efficacy variables in patients treated with NMS-01940153E will be performed if sufficient data are collected.

Graphical display of AFP levels during the study will be used to support data interpretation.

Exploratory analyses on biomarkers/molecular alteration in blood and tumor at baseline will be conducted based on the completeness of data collected.

11. APPENDICES

The appendix “TLGs Mock-ups and Algorithms” is provided as a separate document.

